The rationale for the use in prevention of products useful for the treatment of pressure injuries is also described in the 2013 systematic review (Moore 2013). The incidence of PD is probably reduced through the ability of foam dressings to redistribute mechanical forces. The Guidelines of the European and United States National Pressure Ulcer Advisory Panels (EPUAP and NPUAP) also suggest that the use of foam dressings may protect parts of the body at risk of stretch injuries. The market offers different types of advanced dressings compared to the material they are made of (hydrocolloids, polyurethane foams), their thickness (single or multi-layer) and their dimensions.

Various in vitro comparative studies are available where the different abilities of the main brands of dressings are compared with the pressure redistribution (Call 2015; Matsuzaki 2015; Miller 2015), liquid management (Young 2007) and shear forces (Levy 20015 and Levy 20016) which are the main causative factors of PD development (NPUAP 2014). In these in vitro studies the material that seems to be most effective is polyurethane foam (Matsuzaki 2015; Miller 2015), especially multilayer (Black 2015).

Two systematic reviews published in 2013 and 2014 then evaluated the efficacy on patients of using advanced multi-layer polyurethane dressings in prevention to reduce the incidence of pressure injuries (Clark 2014; Moore 2013). The results of both systematic reviews, although in favor of the use of dressings, are considered by the authors to be inconclusive due to the weakness of the study design found and therefore the high risk of bias. Both reviews concluded by soliciting the production of methodologically more rigorous clinical studies (Clark 2014; Moore 2013). Recently, some trials have been published which confirm the preventive efficacy of polyurethane multilayer foams (Santamaria 2015; Kalowes 2016; Forni 2018; Santamaria 2018) but the populations investigated are very specific, limiting the generalizability of results.

AIM

The aim of the present study was to assess whether the application of a multilayered dressing made of hydrocellular polyurethane foam conformed to the sacral area (MSP) in addition to standard preventive care reduces the rate of pressure ulcer (PU) and their severity in population at risck admitted in acute care Hospital.

Study endpoint

Primary Endpoint

Incidence of PD to the sacrum of any category detected during the first 7 days of hospitalization.

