The 7-day cut off derives from the data in the literature with respect to the average times of onset of the lesions (4th day in the medical field, 5° in the surgical field and 3° in the intensive care unit) with standard deviations that allow to affirm that after 7 days in the acute patients the PD event is extremely rare (Palese 2017; Chiari 2017; Santamaria 2015). PD is defined as a damage to the skin and underlying tissues due to pressure, stretching or friction or a combination of these factors (NPUAP 2014). The incidence of PD is represented by the PD who develop during hospitalization and are not present when the patient is admitted. The injuries will be classified according to the classification defined by the guideline prepared by NPUAP 2014. (attachment).

Secondary Endpoints:

- Incidence of PD to the sacrum category ≥ II ° according to the NPUAP scale
- Skin irritation / damage due to adhesive dressing
- Day of onset of the PD
- Number of dressings used
- Number of patients who stop treatment due to discomfort caused by the dressing (withdrawal)

Other study variables / data collected

- Gender
- Age

- Origin of the patient: first aid, another ward or facility, Short Observation (OBI), Home
- Pregressed (healed) PD to the sacred
- Patient risk level measured with the Braden scale (Pancorbo-Hidalgo PL 2006)
- Days in the study
- Use of the diaper
- Use of the bladder catheter
- Use of anti-decubitus surface (static, preventive dynamics, curative dynamics and air release)
- Daily presence of the caregiver (presence at least during a meal, never, always)

Study Population

Inclusion Criteria:

- Patients at risk of developing PD measured with the Braden scale (Braden \leq 16) with intact sacral skin and / or with signs of healing from previous sacral lesions.
- Patients or legal guardians who consent to the study
- Adult patients
- . Male and female gender
- Expected hospital stay and / or life expectancy > 72 hours
- Patients hospitalized for no more than 24 hours

Exclusion criteria:

- Patients with known allergy to the products under study or with dermatological pathologies that prevent the use of topical products
- Patient with, upon entering the ward, advanced preventive dressing in the sacral region

Design

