Trial randomizzato e controllato di superiorità in cieco (elaborazione dati) a gruppi paralleli con rapporto di allocazione di 1:1 con randomizzazione a blocchi di 10 e bilanciati per reparto e per area. Non è possibile la cecità degli outcome assesor in quanto nei pazienti del gruppo sperimentale resta spesso una traccia cutanea della presenza della schiuma (impronta cutanea).

Randomized controlled superiority trial (blinded only data processing) with parallel groups.

Allocation ratio of 1: 1 with randomization in blocks of 10 and balanced by department and

by area. The blindness of outcomes assesor is not possible as in the patients of the

experimental group there is often a cutaneous trace of the presence of the foam (skin

impression).

Materials and methods

Areas involved

Surgical Area: general or specialist surgery departments.

Medical Area: geriatrics or neurology or internal medicine departments.

Intensive Area: intensive care or intensive care units.

For each area of each participating center a sample of 40 subjects is expected, randomization

will be done by areas.

Intervention:

Application of MSP in the sacral region within 24 hours of admission and replaced when it

comes off, gets wet or gets dirty in addition to standard preventive care (see below).

MSP is a multilayer foam consisting of: a multi-layered dressing consisting of a polyurethane

foam and a super-absorbent hydrocapillary pad, two layers of polyurethane film, one external

and one internal, and a pressure-sensitive adhesive (PSA) that holds together the two

absorbent layers. The last layer, in contact with the lesion and the skin, is in delicate adhesive

silicone, non-adherent, perforated.

The foam must be raised to the margins at least once a day to check the condition of the

underlying skin. If on the seventh day after randomization the patient is still hospitalized,

after the inspection of the skin, the data collection form (CRF) is closed and the study

concluded.

The medication will be provided free of charge for all the subjects in the studio by the

manufacturer. The company will only supply the dressings. A written agreement was signed

in which the company agrees to provide free samples of the product being studied without

5 di 18

affecting in any way the methodology of drafting the protocol, conducting the study, analyzing the data and publishing the results.

Comparison:

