- At discharge or on the appearance of pressure lesion on the sacrum ≥ 2nd category, the CRF is closed and the patient ends the study. If the patient has developed PD the treatment of the lesion will be performed according to the hospital policy.
- The medication will be removed, however, no later than the first 7 days of admission after which the patient ends the study.

Study exit criteria

- Withdrawal of informed consent before randomization
- Not randomized within 24 hours of admission

Conclusion of the study in the single recruited subject

- Withdrawal of consent after randomization
- The appearance of irritation to the skin caused by the dressing. The dressing is removed, reported in CRF and irritation treated as per hospital policy.
- At the request of the patient due to discomfort due to preventive medication.
- On discharge / death / transfer to ward not involved in the study before the 7th day after randomization
- After 7 days from randomization in the absence of PD to the sacrum
- The appearance of pressure injury to the sacrum higher than the first category

Sample size

From a randomized monocentric study of at-risk patients with a hip fracture where polyurethane foams were used in prevention, the incidence in the experimental group was 4.5% while in the control group of 15.4%. Similar deltas had also been identified in other trials in intensive care patients. Assuming similar results in the population subject of the present study and taking into account an alpha error of 0.05 and a beta error of 20%, it is necessary to enroll at least 228 patients at risk. In order to allow analyzes by subgroup (see the "statistical analysis" section) the sample size must be guaranteed for each area (medical, surgical, intensive).

Taking into account also a possible loss at the follow-up of 10% and also assuming a 10% withdrawal rate, the necessary sample will be 280 patients per area and therefore a total of 840 patients (420 per arm). Each hospital involved will enroll 40 patients per area involved in that specific hospital.

Randomization

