- If instead the MSP is present and the patient belongs to the control group, the dedicated nurse reports the violation of the CRF randomization but leaves the MSP and treats the patient as reported for the experimental group. At the analysis of the results, if these violations have occurred, we will proceed in addition to the analysis for Intention to Treat also for Protocol.
- If the patient is replaced by a different MSP (different brand) than the one in the studio, the dedicated nurse replaces it and marks the problem in CRF.

Safety / risk assessments for participants:

Patients are treated according to protocols and policy already in place (prevention and treatment of pressure injuries), and always in strict compliance with the Good Clinical Practice (GCP), there are no additional risks for the participants. The patient who eventually develops pressure ulcer will be treated as per hospital policy. If the patient develops a category I sacral lesion remains in the study. The event is marked in the data collection form (CRF). The rationale for this permanence involves both the difficulty in the differential diagnosis with skin redness (Sterner 2011) and the need to detect the secondary outcome

"Incidence of PD to the sacred category \geq II ° according to the NPUAP scale". The treatment of a category I injury involves the use of creams or at the most of ultrathin advanced dressing. If used in the control group patient it will be reported in CRF. If the patient belongs to the experimental group, no additional action is necessary.

Duration of the study

The project lasts a total of 12 months which includes the training of the staff of the centers involved, the recruitment of patients, the collection and processing of data. The time per patient is 7 days or until discharge if it occurs before the seventh day of admission. The date of the start of the trial will be considered to be the approval of the Ethics Committee for each center.

The timing of the study includes the following subdivision:

- Months 1 training of the centers involved
- Months 2- 6- patient enrollment and database implementation
- Months 7-12 Data analysis and results dissemination

Ethical and Administrative Aspects

Informed consent

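### An ulcer labelled dressing irritation drops out of the primary count almost only in the dressing arm, and no planned analysis bounds the effect

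*Combined protocol and SAP*

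**What the plan says.** All references are to the combined protocol and SAP.

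- **Primary Endpoint:** "Incidence of PD to the sacrum of any category detected during the first 7 days of hospitalization". Category I therefore counts.
- **Definition, same section:** "PD is defined as a damage to the skin and underlying tissues due to pressure, stretching or friction or a combination of these factors". The definition rests on cause. Injuries are to be graded by the NPUAP 2014 classification, in an attachment that is not reproduced.
- **Secondary Endpoints:** "Skin irritation / damage due to adhesive dressing" is listed as a separate outcome.
- **Conclusion of the study in the single recruited subject:** one of the events that ends participation is "The appearance of irritation to the skin caused by the dressing. The dressing is removed, reported in CRF and irritation treated as per hospital policy".
- **Safety / risk assessments for participants:** "If the patient develops a category I sacral lesion remains in the study". One of the two reasons given is "the difficulty in the differential diagnosis with skin redness".
- **Design:** "The blindness of outcomes assesor is not possible as in the patients of the" experimental arm the foam often leaves a mark on the skin. Only data processing is blinded.
- **Possible deviations from the protocol:** a control patient found wearing the dressing keeps it and is handled like the experimental arm.
- **Statistical analysis:** intention to treat, Fisher's exact test, and incidence for every dichotomous variable. A per-protocol analysis is added if control patients were found with a dressing.

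**The concern.** For a control patient, a doubtful change in sacral skin is either a pressure injury or not an event. For a dressed patient there is a further label, dressing irritation. The two named labels lead to opposite results. Category I is a primary event and the patient is followed on. Irritation is not a primary event and the patient leaves. The text gives no criteria for separating them and no adjudication, and the person who decides knows the arm.

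An ulcer recorded only as irritation is lost from the primary count, and with few exceptions the loss falls in the dressing arm. The exit also ends observation, so a later sacral ulcer, including one of category II or higher, can go unseen. What is at stake is the relative risk and number needed to treat on the primary endpoint, and the per-area comparisons for which the trial is sized.

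**Working it through.** **1. The plan's own figure.** Inputs from Sample size: 15.4% control, 4.5% experimental, alpha 0.05 (taken as two-sided), power 80%. With unpooled variance:

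n per arm = (1.960 + 0.842)² × (0.154×0.846 + 0.045×0.955) / 0.109² = 114.5, or 229 in total, against 228 stated.

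Allowing for two 10% losses, 228/(0.9×0.9) = 281.5, against 280 stated per area. The figures reproduce, and nothing in this point disputes them.

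**2. Does any planned analysis correct the label?**
- Intention to treat fixes who is in the denominator. It does not change how a lesion was classified, and it does not supply an outcome that was never observed.
- The per-protocol analysis is triggered by control patients found with a dressing, not by irritation exits.
- The incidence of irritation as a secondary endpoint shows how many such cases there were, but not how many were ulcers.

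**3. Size, by illustration.** No irritation rate is given, so the number of hidden events k is an assumption. Expected counts with 420 per arm: 420×0.045 = 18.9, taken as 19; 420×0.154 = 64.7, taken as 65. With 140 per arm in one area: 6.3, taken as 6; 21.6, taken as 22. Losses are ignored. Relative risk = (counted + k)/control events, and the test is two-sided Fisher.

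| Setting | k | True dressing events vs control | k as share of true dressing events | RR | p |
|---|---|---|---|---|---|
| Overall | 0 | 19 vs 65 | 0% | 0.29 | 1.2×10⁻⁷ |
| Overall | 5 | 24 vs 65 | 21% | 0.37 | 5×10⁻⁶ |
| Overall | 10 | 29 vs 65 | 34% | 0.45 | 0.0001 |
| Overall | 21 | 40 vs 65 | 52% | 0.62 | 0.012 |
| Overall | 26 | 45 vs 65 | 58% | 0.69 | 0.052 |
| One area | 0 | 6 vs 22 | 0% | 0.27 | 0.0023 |
| One area | 4 | 10 vs 22 | 40% | 0.45 | 0.0375 |
| One area | 5 | 11 vs 22 | 45% | 0.50 | 0.063 |

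The number needed to treat, 420/(65 − events), is 420/46 = 9.1 at k = 0 and 420/25 = 16.8 at k = 21.

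**4. Reading the table.** As a share of the arm, 26/420 is 6.2% and 5/140 is 3.6%, which sounds small. As a share of true ulcers in the dressing arm they are 58% and 45%, which is a high rate of mislabelling. The effect estimate is disturbed well before significance is lost.

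The same rows serve for the proposed bound: with k irritation exits and no recorded pressure injury, the worst-case table is (19 + k) vs 65.

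**The case against.** The case on the other side is substantial.

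- **Irritation is not ignored.** It is a listed secondary endpoint, entered in the CRF, and its incidence will be reported. A reader might infer that the results would hide the problem completely. They would not: anyone could add the irritation count to the primary count. What is missing is the category of those lesions and a prespecified bound. This stands.
- **Direction.** A reader might infer a bias that must favour the dressing. The documents do not support that. The Design section says the foam often leaves a skin mark, and calling that mark or an adhesive reaction category I would count against the dressing. An unblinded nurse can also dismiss redness in a control patient. Only the specific error, an ulcer recorded as irritation, has a clear direction.
- **Not strictly one arm.** Control patients found with a dressing are an exception.
- **Overlap is inferred.** The documents never describe dressing irritation as redness, and they do not say the two labels exclude each other. The CRF and the NPUAP attachment are not reproduced, so a category field may already exist.
- **Size.** The scenarios that overturn significance need about half of true dressing-arm ulcers to be mislabelled. With 5 hidden events the result is hardly in doubt.
- **Disclosure.** Unblinded assessment is stated openly and with a reason.

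These points limit the claim but do not remove it. Disclosing unblinded assessment does not separate the two labels, and reporting the irritation count does not reclassify any lesion.

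**Conclusion.** The concern holds as a gap in how the primary event is classified. Two labels with opposite consequences may apply to similar sacral skin, an unblinded nurse chooses, and one label is available essentially only in the dressing arm. An ulcer recorded as irritation lowers primary incidence in that arm and ends its observation, and no planned analysis bounds the effect.

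The net direction is not certain and the size is unknown. The illustrations assume planning rates, full follow-up, two-sided tests and errors in one direction only. On those terms, mislabelling about a fifth of true dressing-arm ulcers moves the relative risk from 0.29 to 0.37, and about half moves it to 0.62. Reversing overall significance needs 58%, and reversing it within one area needs 45%. The documents do not show that mislabelling on that scale would occur. The case for acting is that a lesion left ungraded at exit may not be recoverable afterwards, while recording it costs almost nothing.

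**What to change.** 1. At the inspection where irritation is recorded, also record an NPUAP category (none / I / II or higher) in a separate CRF field, if the CRF does not already have one. Count as a primary event any lesion judged to be a pressure injury under the protocol's own cause-based definition, even when irritation is recorded too. Counting lesions regardless of cause would conflict with that definition.
2. Prespecify one sensitivity analysis of the primary endpoint in which every irritation exit without a recorded pressure injury counts as a primary event. Label it a worst-case bound against the dressing. For the primary endpoint it also covers ulcers that might have appeared after the exit. It does not do so for the category II or higher secondary endpoint.

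The cost is one field at an inspection already made daily, and one extra table. Sample size and patient care are unchanged. The downside is that the bound is one-sided: it will count some true adhesive reactions as ulcers and may make the dressing look less favourable than it is, so it should stand beside the primary result and not replace it.

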At the Research Center for Health Professions of the Rizzoli Orthopedic Institute in Bologna (coordinating center), using the site: www.randomization.com, a randomization list will be generated in blocks of 10. A sequence of opaque envelopes will be prepared with outside a progressive number. Inside the envelope a label will be placed that will contain the words "yes" or "no", according to the sequence indicated by the generated list.

The envelopes will always be sealed at the Research Center and the list kept under lock and key. The envelopes will be placed in a dedicated box and delivered to the nursing research manager of the hospitals involved in the study. In each ward/area a reference nurse will be identified and 40 envelopes delivered.

Statistical analysis

The analysis of the results will be carried out for Intention to Treat.

All continuous data will be expressed in terms of average and standard deviation. One Way ANOVA will be used to evaluate the differences between the averages of the experimental and comparison group. If the Levene test for homogeneity of variance were significant (p <0.05), the Mann Whitney test will be used. For all dichotomous variables the incidence, relative risk, relative risk reduction and number needed to treat will be calculated. The exact

Fisher test will be used to evaluate the differences between the incidences of different outcomes between the experimental group and the control group.

Subgroup analysis:

- by area of belonging (medical, surgical or intensive)
- by risk level according to the Braden classification: Severe (total score 9); High Risk (10-12) Moderate Risk (13-14); low Risk (15-16). (Pancorbo-Hidalgo PL 2006)
- by origin (domicile vs. other settings)

For all tests, a p <0.05 will be considered significant.

The statistical analysis will be done using the "Statistical Package for the Social Sciences" (SPSS) software version 15.0 (SPSS Inc., Chicago, USA)

Possible deviations from the protocol and / or critical issues and related behavior to be followed in all situations

- If the dedicated nurse, during the daily inspection, realizes that the sacral MSP (in the patients of the experimental arm) has been removed without being positioned anymore, he provides to reposition it, marking in the CRF that the patient for that day remained without.

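### The 80% power claimed for each area does not hold for the planned Fisher test, and falls far lower if the Background's medical and general surgical incidences apply

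*Combined protocol and SAP*

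**What the plan says.** The Sample size section takes 15.4% (control) and 4.5% (dressing) from a single-centre hip-fracture trial, with alpha 0.05 and beta 20%, and concludes that "it is necessary to enroll at least 228 patients at risk". It carries these rates to every area: "Assuming similar results in the population subject of the present study". For intensive care it adds "Similar deltas had also been identified in other trials in intensive care patients". To permit subgroup analyses it requires that "the sample size must be guaranteed for each area (medical, surgical, intensive". Allowing for "a possible loss at the follow-up of 10% and also assuming a 10% withdrawal rate", it arrives at "the necessary sample will be 280 patients per area and therefore a total of 840 patients (420 per arm".

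The Statistical analysis section states "The analysis of the results will be carried out for Intention to Treat" and, for incidences, "Fisher test will be used to evaluate the differences between the incidences of different outcomes". It lists area among the subgroup analyses and applies p<0.05 to all tests. Neither section says whether tests are one- or two-sided.

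The Background cites incidences of 6.5% in the medical field, 8.8–9.2% in surgical patients in general, 11.9–19.2% in orthopaedic patients and 13.1% in intensive care, within an overall range of 7% to 71.6%.

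**The concern.** The trial is three times the size of a single comparison so that each area can be read on its own. That is worthwhile only if each area has roughly the power stated. There are two reasons for doubt. The size appears to come from a formula that is less demanding than the planned test. And one control rate, from a higher-risk orthopaedic group, serves areas for which the protocol itself cites much lower rates.

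What is at stake is how a non-significant area result is read. Someone relying on 80% power could take it to mean that the dressing does not work in medical or surgical wards, when the area was never large enough to show the planned effect.

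**Working it through.** **Inputs.** Sample size section: 15.4% vs 4.5%, alpha 0.05, power 80%, 228 evaluable and 280 enrolled per area, two 10% losses. Design section: 1:1 allocation. Statistical analysis section: Fisher's exact test. Background: the area incidences. Two-sided testing is assumed, because the two-sided unpooled formula gives the stated 228, while one-sided formulas give 180 (unpooled), 186 (pooled) or 220 (pooled with continuity correction).

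**Reproducing the 228.** Unpooled normal approximation:

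n per arm = (1.96 + 0.8416)² × (0.154×0.846 + 0.045×0.955) / 0.109² = 7.849 × 0.17326 / 0.011881 = 114.5, or 228.9 in total.

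The 228 is therefore not an arithmetic slip. The two-sided pooled formula gives 236, or 270 with continuity correction.

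**Losses.** 280 × 0.80 = 224; 280 × 0.9 × 0.9 = 226.8. The section's own allowances leave about 224–227 analysed.

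**Fisher power at the planning rates.** Binomial probabilities were summed over all 2×2 tables with two-sided Fisher p<0.05:

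| Analysed per area | Power |
|---|---|
| 224 | 72.9% |
| 226 | 73.4% |
| 228 | 73.9% |
| 252 | 78.9% |
| 256 | 79.7% |
| 258 | 80.1% |
| 280 | 84.1% |

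The target is kept only if no more than 22 of 280 (7.9%) are missing from the analysis.

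**Fisher power at other control rates.** The planned relative risk is 4.5/15.4 = 0.292 and the planned difference is 10.9 points. At 6.5%, 8.8% or 9.2% a 10.9-point fall is impossible, because it exceeds the control rate. Power with 228 | 280 analysed:

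| Control incidence | Constant RR 0.292 | Constant 10.9-point difference |
|---|---|---|
| 6.5% (medical) | 28% \| 36% | not attainable |
| 8.8% (surgical, general) | 44% \| 52% | not attainable |
| 9.2% (surgical, general) | 46% \| 55% | not attainable |
| 11.9% (orthopaedic, low) | 60% \| 70% | 94% \| 97% |
| 13.1% (intensive) | 65% \| 76% | 87% \| 93% |
| 19.2% (orthopaedic, high) | 85% \| 93% | 61% \| 71% |

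**Effect needed for 80% power, whatever the scale.** At 6.5% with 228 analysed no effect is enough: zero expected events on the dressing still gives only 76%. With 280 the relative risk must be about 0.05. At 8.8–9.2% it must be about 0.08–0.10 (228) or 0.14–0.15 (280), against the planned 0.29.

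**Control rate needed for 80% at RR 0.292.** About 17.3% with 228 analysed, 15.7% with 252 and 14.2% with 280.

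**What an area result near the planned relative risk would look like.** Counts are the expected values, rounded:

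| Control rate | Events | Per arm | Fisher p |
|---|---|---|---|
| 6.5% | 7 vs 2 | 114 | 0.17 |
| 6.5% | 9 vs 3 | 140 | 0.14 |
| 8.8% | 10 vs 3 | 114 | 0.083 |
| 8.8% | 12 vs 4 | 140 | 0.069 |
| 9.2% | 13 vs 4 | 140 | 0.042 |

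**Pooled comparison, constant RR.** With 336 per arm (420 × 0.80), Fisher power is 83% at a 6.5% control rate and 95% at 9.5%. With 420 per arm it is 91% and 98%. The 9.5% is about the mean of the three area figures: (6.5 + 9.0 + 13.1)/3.

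**The case against.** The strongest defence has three parts.

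First, the analysis is by intention to treat. Early discharge, transfer or discomfort ends a patient's participation but is not listed as an exclusion from analysis, and the skin is inspected daily, so most such patients have outcome data. If all 280 count, power at the planning rates is 84%. This stands as a possibility. But the Sample size section inflates because it expects to lose patients, the Method section removes patients whose dressing is not applied within 24 hours of admission, and no rule is given for incomplete follow-up. Above about 8% missing, the 80% is lost.

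Second, the Background incidences are unmatched proxies. They are not stated to be sacral only, limited to Braden ≤16 or counted over 7 days, and the study cited for 6.5% has a title that refers to incidence density of unavoidable ulcers. Rates in an at-risk population may be higher. This also stands, and it makes the 28–36% and 44–55% conditional. It does not support a single rate of 15.4% in every area, and it is a reason to show how power depends on the control rate.

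Third, the surgical area includes specialist wards. At the orthopaedic rates, constant-RR power runs from 60–70% to 85–93%, and not every plausible surgical result would miss significance (13 vs 4 of 140 gives p = 0.042). That is correct, so no shortfall is claimed for a surgical area weighted to such wards.

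**Conclusion.** The concern holds. At the protocol's own rates, the 80% per area becomes 74% under the planned test with 228 analysed, and 73–74% after the protocol's own losses. It is met only from 258 analysed upward. This part needs no outside assumption beyond two-sided testing.

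The larger shortfall, 28–36% (medical) and 44–55% (general surgical), rests on two assumptions: that the Background incidences apply to this population, and that the relative risk is constant at 0.292. In the medical area with 228 analysed, the first assumption alone is enough to miss 80%.

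No firm claim is made for intensive care, where the answer depends on whether the similar deltas mean a constant relative risk (65–76%) or a constant difference (87–93%), which the section does not say. The pooled primary comparison is sound. The point should be fixed, but it does not threaten the main result.

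**What to change.** Keep 840 patients and Fisher's exact test, and make three changes:

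1. In the Sample size section, name the pooled comparison of the primary endpoint as the powered, confirmatory analysis and state its Fisher power.
2. Replace the implied 80% per area with a short table of Fisher power for 228 and 280 analysed, over control incidences from about 6.5% to 20% or more. State whether a constant relative risk or a constant difference is assumed.
3. In the subgroup plan, add 95% confidence intervals to the relative risks already planned, and say that a non-significant area result is not evidence of no effect.

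The cost is some rewording, one small table and a sentence in the subgroup plan. The downside is that the stated per-area power becomes less favourable, and the claim that each area is separately powered is dropped or made conditional on the control rate.
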